### **Exclusion criteria:**

- Fluoroscopy guided procedures performed on pediatric patients ( $< 16$  years old)
- Fluoroscopy guided procedures performed on a fixed interventional radiology imaging system even if it was located in the operating theater.
- Medical procedures performed using both a mobile x-ray system and a fixed CT scanner
- Medical procedures performed using a mobile intra-operative CT scanner

### **Data collection**

Data will be collected using a password-protected Excel spreadsheet. This excel file will be sent to all the participating institutions at the beginning of data collection. Every institution will send the excel file completed with anonymized data to the scientific responsible of the study through the secure email server of the APHP institution. Data collection period is set to 6 months.

Collected data have been organized into 4 categories:

- Data regarding the x-ray equipment and available on the quality controls (QC) reports : Year of construction, image detector type, size of the smaller field,

difference between the displayed and measured KAP for the smallest field, size of the biggest field, difference between the displayed and measured KAP for the biggest field, size of the largest field adapted to the size of the phantom, difference between displayed and measured air kerma available in the last QC report, date of the last external QC previous to the procedure. Also, participating institution should precise whether if the x-ray equipment was connected to a Dose Archiving and a Communication system (DACS)

- Data regarding the patient (Optional) : Weight and height (provided from the equipment or given by the medical team)
- Data regarding the procedure: specialty, additional information about the procedure, size of the most used field for the concerned procedure. These data are provided by the medical team.
- Technical and dosimetric data available on the x-ray equipment : total KAP, Total air kerma, total number of image frames, fluoroscopy mode, fluoroscopy pulse rate, fluoroscopy time, dosimetric data specific to the O-arm equipment.

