## **Objectives**

### **Main goal:**

Establish dosimetric reference levels, in terms of KAP (Kerma-Area-Product)

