#### **Outcomes:**

The main goal of this study is to publish descriptive statistics (mean, standard deviation, median, 1st quartile, 3rd quartile) for each dosimetric data (KAP, fluoroscopy time, kerma, etc..) and for each category of surgery procedures. Results will be presented with a 95% confidence interval.

Moreover, correlation analysis between several variables as indicated previously in the goal section will be done. The differences between detector and equipment technologies will be also studied using appropriate statistical tests.

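### Does the protocol let meter error pass into the KAP reference levels by recording displayed-versus-measured differences and stating no use for them?

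*Protocol*

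**What the plan says.** The main goal is reference levels in KAP; fluoroscopy time and air kerma are secondary (Protocol, Main goal and Secondary goals). The Data collection section gives the source of the outcome as "Technical and dosimetric data available on the x-ray equipment : total KAP".

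The same section lists equipment variables from QC reports: "difference between the displayed and measured KAP for the smallest field", "difference between the displayed and measured KAP for the biggest field", "difference between displayed and measured air kerma available in the last QC report", the sizes of those fields and the date of the last external QC. The procedure data add "size of the most used field for the concerned procedure".

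The Outcomes section promises "publish descriptive statistics (mean, standard deviation, median, 1st quartile, 3rd quartile) for each dosimetric data" with 95% confidence intervals, correlation analyses, and tests of differences between detector and equipment technologies. The Secondary goals include variability between sites. None of these sections mentions the QC differences, either to apply them or to set them aside.

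**The concern.** The product of the study is a set of published numbers against which other sites will judge their practice. A KAP value read from a machine carries that machine's meter error. At a given field size this error is largely common to all cases on the machine, so 15 to 30 cases per institution do not average it out.

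If raw readings were analysed, three things could follow:
- a shared error would move every reference level by the same proportion, and the confidence interval would not show it;
- errors that differ between machines would add to the apparent variability between sites;
- errors that differ on average between technologies would look like a difference in dose.

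The protocol collects what is needed to examine this and states no use for it, which looks like an omission in the definition of the main outcome.

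**Working it through.** **What is written.** Three readings of the protocol are possible: raw readings are analysed; readings are corrected by the QC difference; or the QC difference screens machines or feeds a sensitivity analysis. The text excludes none of them. The list of variables favours the second or third, because the error at two field sizes, those field sizes and the most used field have little purpose together except to check or correct the reading.

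**Size of the effect.** The protocol states no figure for meter error, so there is none to reproduce and every error size below is an assumption. Write displayed KAP = true KAP × (1 + e).

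*Institutions per procedure type.* The stated totals imply 11490/15 = 22980/30 = 766 institution-by-procedure pairs, and 766/62 = 12.35 institutions per type. The 766 is inferred; the protocol does not state it.

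*Shared error.* If e is the same for all machines, every mean, median and quartile scales by 1 + e: 1.10 for +10%, 1.25 for +25%.

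*Errors around zero.* Simulation with log-normal KAP, log-SD 0.8 within and 0.5 between sites, 12 sites × 15 cases, one machine per site, and e uniform within the limits. The ratio is displayed to true third quartile.

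| Limits of e | Pooled third quartile: mean ratio (95% range) | Third quartile of site medians: mean ratio (95% range) |
|---|---|---|
| ±10% | 1.00 (0.942 to 1.059) | 1.001 (0.925 to 1.075) |
| ±25% | 0.997 (0.883 to 1.111) | 1.004 (0.835 to 1.179) |

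There is almost no shift, only added spread. With 30 cases per site the pooled ranges are 0.951 to 1.049 and 0.892 to 1.102.

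*Added standard error of a mean level.* Meter error alone contributes SD/√12.35. The comparison is the standard error already present on the log scale under the same assumed spreads: √(0.5²/12.35 + 0.8²/(12.35 × 15)) = √(0.02024 + 0.00345) = 0.154, about 15%. Combining the two in quadrature:

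| Assumed SD of e | SD/√12.35 | Combined standard error | Increase |
|---|---|---|---|
| 10% | 2.8% | √(0.0237 + 0.0008) = 0.157 | about 2% |
| 20% | 5.7% | √(0.0237 + 0.0032) = 0.164 | about 7% |
| 30% | 8.5% | √(0.0237 + 0.0073) = 0.176 | about 14% |

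*Variability between sites.* Adding the same SDs to a between-site log-SD of 0.5 gives √(0.25 + 0.01) = 0.51, √(0.25 + 0.04) = 0.54 and √(0.25 + 0.09) = 0.58.

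*Equipment comparison.* If two technologies had opposite errors of ±10%, the false ratio would be 1.10/0.90 = 1.22; at ±25% it would be 1.25/0.75 = 1.67. With 6 against 6 machines, no true difference and a site-level t-test, simulated false rejection rises from about 5% to about 10% and 31%. This needs errors fully aligned with technology.

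**The case for a change.** The strongest case for a change is that whether the main outcome is a displayed or a corrected quantity belongs to its definition. Two analysts could follow the Outcomes section and publish different levels, and a choice made after seeing the data would be open to selection. Since the inputs are on the collection form, a corrected main analysis with an uncorrected sensitivity analysis would cost only analysis work.

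Part of this stands: the protocol states no rule, and a reader of the results will need to know which quantity was used. The rest is weaker.

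- How raw readings are corrected, screened or checked is a derivation rule that an analysis plan commonly holds. The protocol cannot be faulted for leaving it there.
- The inputs support a correction less well than they seem to. The protocol gives neither sign nor unit for the differences. The most used field is one typical value reported by the medical team, while zoom and magnification vary enough to be a secondary goal. The QC may be of any age. Interpolating between two QC points at one typical field could therefore add error as well as remove it.
- If the error changes with field size, as such interpolation presumes, it is not one constant per machine, and a single correction only approximates it.
- For sites that compare their own console readings with the published level, displayed values have a case of their own. Reasonable experts would differ on which should be the main analysis.

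**Conclusion.** No change to the plan is called for. The factual core is sound: the QC differences are collected, and neither the goals nor the Outcomes section says how they are used. But the protocol does not commit to uncorrected readings, and its own list of variables points to a calibration check or correction. This is a gap in detail that analysts can fill sensibly, in an analysis plan or when reporting, by saying which quantity the levels rest on.

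The harm is conditional. Error scattered around zero leaves the pooled third quartile nearly unbiased and, at an assumed SD of 10% to 30%, raises the standard error of a mean level by about 2% to 14% of itself. These figures rest on assumed log-normal spreads, one machine per site and about 12 institutions per procedure type. A proportional shift, or a false difference between technologies, needs an error that is common to all machines or aligned with system family. The protocol gives no evidence of either.

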#### **Outcomes:**

The main goal of this study is to publish descriptive statistics (mean, standard deviation, median, 1st quartile, 3rd quartile) for each dosimetric data (KAP, fluoroscopy time, kerma, etc..) and for each category of surgery procedures. Results will be presented with a 95% confidence interval.

Moreover, correlation analysis between several variables as indicated previously in the goal section will be done. The differences between detector and equipment technologies will be also studied using appropriate statistical tests.

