### **Secondary goals:**

- Reference levels in terms of fluoroscopy time and air kerma
- Analysis by the procedures details (impact of different techniques, instruments and materials, etc...)
- Assessing inter-site variability
- Correlation between KAP and BMI, fluoroscopy pulse rate and mode

- Ratio between fluoroscopy and radiography doses
- Effect of zoom and magnification on the dose
- Institution -type distribution of doses
- Impact of the surgical specialty on the doses delivered for some procedures.

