### **Scope of the study**

**Surgical procedures:** a total of 62 procedures (p=62) belonging to 7 different surgery specialties are involved in this study. Selected specialties are neurosurgery (p=12), orthopedic (p=15), digestive (p=6), urology (p=10), cardiology (p=6), vascular (p=11), multi-specialty (p=2). A brief summary of each procedure will be sent to the participating institution.

**Study type and cohort:** This is a multi-centric prospective study which consists on progressively collecting anonymous data for 15 to 30 procedures from a list of 62 procedures. This study is thus equivalent to a retrospective study. It doesn't require any access to patient medical records nor influence his medical care as the data are only provided by the x-ray system or the medical team.

In order to reach a good compromise between satisfactory statistical power and achievable database, 15 to 30 procedures per surgery type and per institution would be suitable for the study. This is consistent with the previous published studies and recommendations (ICRP, French legislation). Moreover, limiting the number of procedures to this range (15-30) will ensure enrollment of homogeneous cohorts between participating institutions.

73 health institutions of different categories (University hospital, clinic, cancer center, etc..) confirmed their participations to the study. Hence, the minimal number of procedure regardless of the procedure type would be 11490 and the maximal number would be 22980.

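### Must the protocol name the institution as the unit of analysis for its 95% confidence intervals and equipment tests?

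*Protocol*

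**What the plan says.** Under Scope of the study, the protocol states that "15 to 30 procedures per surgery type and per institution would be suitable for the study". It adds that "73 health institutions of different categories (University hospital, clinic, cancer center, etc..) confirmed their participations to the study", and that "the minimal number of procedure regardless of the procedure type would be 11490 and the maximal number would be 22980".

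Under Data collection, detector type is recorded with the equipment: "Data regarding the x-ray equipment and available on the quality controls (QC) reports : Year of construction, image detector type". It therefore describes a machine and not an individual procedure. Each institution completes and returns its own spreadsheet.

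The Outcomes section lists mean, standard deviation, median and quartiles for each dosimetric quantity and "for each category of surgery procedures. Results will be presented with a 95% confidence interval". It then says that "The differences between detector and equipment technologies will be also studied using appropriate statistical tests". It gives no interval method, no named test and no unit of analysis.

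Among the Secondary goals is "Assessing inter-site variability", together with the distribution of doses by type of institution.

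**The concern.** Sampling 15 to 30 procedures of one type from each institution is cluster sampling. Procedures at one site share machines, operators, settings and habits, so their doses are likely to be correlated. The Outcomes section attaches intervals to per-category statistics without mentioning site, and the quickest way to compute them is to pool all procedures of a type and ignore where they came from.

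Two things would be at stake. The published interval around a reference level would understate how far that level could move with another set of institutions. That matters because physicists and surgeons elsewhere are meant to judge their own practice against it. And a detector or equipment effect could be a chance difference between a small number of sites, presented as a finding from hundreds of procedures.

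**Working it through.** **Inputs from the protocol.** 15 to 30 procedures per type and institution; 62 procedure types; 73 institutions; totals of 11,490 and 22,980; 95% confidence level.

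**Assumptions.** The ICC of log dose is not given, so it is varied. A two-sided 5% test level is assumed, as none is stated. Log dose is taken as normal with a random institution effect.

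**Step 1: the protocol's own totals.** 11,490 / 15 = 766 and 22,980 / 30 = 766. The two ends agree on 766 institution-by-type series, a count the protocol does not state. It is not the product of all sites and types (73 × 62 × 15 = 67,890), as expected if each site contributes only some types. The average is 766 / 62 = 12.4 institutions per type; individual types will differ.

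**Step 2: intervals for a mean if site is ignored.** The design effect is DE = 1 + (m − 1) × ICC, where m is the number of procedures per site. Actual coverage of the nominal 95% interval is 2Φ(1.96/√DE) − 1.

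| ICC | DE, m = 15 | Coverage | DE, m = 30 | Coverage |
|---|---|---|---|---|
| 0.01 | 1.14 | 93.4% | 1.29 | 91.6% |
| 0.05 | 1.70 | 86.7% | 2.45 | 78.9% |
| 0.1 | 2.40 | 79.4% | 3.90 | 67.9% |
| 0.3 | 5.20 | 61.0% | 9.70 | 47.1% |

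At ICC 0.1 a correct interval is √2.40 = 1.55 to √3.90 = 1.97 times as wide as the naive one.

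**Step 3: third quartile and a between-site test.** Simulation with 12 sites, 15 to 30 procedures each and 4,000 datasets per ICC. The interval is an order-statistic interval that ignores site. The test is a two-sample t test of a factor constant within site, 6 sites against 6. Ranges are over repeat runs.

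| ICC | Third-quartile coverage | Type I error |
|---|---|---|
| 0 | about 96% | about 5% |
| 0.05 | 88–90% | 17–18% |
| 0.1 | 82–83% | 27–29% |
| 0.3 | 63–65% | 49–50% |
| 0.5 | 52–53% | 58–60% |

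**Step 4: the same test when equipment varies within sites.** With 12 sites and both technologies used evenly inside each, and no extra variation between machines, the naive test is at or below its nominal level: 4.6% (m = 15) and 4.5% (m = 30) at ICC 0.05, and 2.4% for both at ICC 0.3. Over-rejection therefore depends on how machines are spread across sites, which the protocol does not describe.

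**Step 5: would a written rule settle it?** A t test on institution means holds its level when the factor is fixed by site (4.5 to 6.2% for ICC 0 to 0.5). But detector type belongs to the machine. With two machines per site carrying different detectors, and assumed variance shares of 0.1 for site and 0.1 for machine, a model with only an institution intercept and t on 10 degrees of freedom still rejects about 14% of the time, against 17% for the naive test. A rule naming the institution alone would not secure 5% in that layout. The right level depends on an equipment distribution that is known only once the data are in.

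**The case for a change.** The strongest case for a change is that this goes beyond a missing method name. The reference level is the main output, and the protocol itself commits to an interval for it. Whether that interval describes only the procedures collected or a level that carries over to other institutions depends on the sampling unit, and the stated purpose points to the second reading. The same holds for whether the level is a quantile of all procedures or of institution-level values. A remedy would take two or three sentences and no new data.

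Much of this stands. The clustering is real, the intervals would be too narrow under any material ICC, and that part does not depend on how equipment is distributed. Nor does over-rejection need complete separation: if 4 of 12 sites use both technologies evenly and the other 8 use one each, the naive test still rejects 13% of the time at ICC 0.05 and 21% at 0.1.

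What does not stand is the step from silence to error. Every harm here is conditional on an analysis that the protocol never says it will do. Nor need the detector tests rest on a dozen sites: the sentence about them is not restricted to one procedure type, so they may pool types across up to 73 institutions.

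**Conclusion.** No change to the protocol is called for. The Outcomes section states nothing false on this point, contradicts no other section and fixes no method that ignores site. Its reference to appropriate tests admits a clustered analysis. Data return by institution keeps the site identifiable, and the inter-site goal shows that the investigators have variation between sites in view. Interval method and unit of analysis are commonly left to an analysis plan, and a competent analyst would fill this gap without difficulty.

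The conditional size is worth knowing: third-quartile coverage of about 90% at ICC 0.05 and 82% at 0.1, and negligible harm at ICC 0.01 (about 95%). These figures rest on an assumed ICC, normal log doses and an average of about 12 sites per type. Ignoring clustering would affect the stated precision of the reference levels, not the computed quartiles. The over-rejection of equipment tests is limited to factors that vary mainly between sites, or between machines that differ for other reasons.

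As an optional note for the analysts: compute the intervals by a cluster-robust method with the institution as sampling unit, and test equipment factors at the level at which they vary, with random effects for institution and for machine within institution.

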#### **Study approval and patients consent**

This study has received the approval of the French Health Researches, Studies and Evaluations Expert committee (CEREEES-TPS 51076bis) on June 2018 and the National Commission for Data Protection and Liberties (CNIL-DR-2018-201) on august 2018. These national committees granted the study an exception from obtaining patients informed consent because it respected the following conditions:

- ✓ Anonymous data collection
- ✓ No codes are attributed to the patients
- ✓ No need and no possibility to access to the patient medical record
- ✓ No risk in identifying the patient afterwards
- ✓ The research could not practically be carried out without the waiver of informed consent.

However, comprehensive and concise information regarding this study will be provided to patients in the form of collective display in the participating departments. This information leaflet mentions the purpose, risks and benefits of the study and informs the patients of the possibility of opposing the use of their data.
